# **SYNOPSIS**

Study Title:	A Phase II Clinical Study of BBI608 in Adult Patients with Advanced Colorectal Cancer		
Study Number:	BBI608-224		
Study Phase:	Phase II		
Study Drug	BBI608, a novel investigational small molecule anticancer drug that targets cancer stem cells.		
Primary Objectives:	To determine the safety and preliminary anti-tumor activity of BBI608 when administered in combination with Cetuximab, or Panitumumab, or Capecitabine in adult patients with advanced colorectal cancer who have failed first and second line treatment.		
	The primary endpoint will be disease control rate, defined as the proportion of patients with a documented complete response, partial response and stable disease (CR + PR + SD) based on RECIST. The secondary endpoints will include progression-free survival (PFS) and overall survival (OS).		
Secondary Objectives:	To determine the pharmacokinetic profile of BBI608 and Cetuximab, or Panitumumab, or Capecitabine when administered in combination.  To determine the pharmacodynamics (biomarkers) of BBI608.  To evaluate tolerability of two dosing regimens of BBI608 by comparing administration of BBI608 at 240 mg twice daily starting dose and escalating to 480 mg twice daily after cycle 1 versus administration of BBI608 at 480 mg twice daily starting dose with dose adjustment permitted.  To evaluate tolerability of BBI608 by comparing prophylactic administration of anti-diarrheal medication versus as needed administration of anti-diarrheal medication. The tolerability will be assessed using adverse event profile and achieved dose intensity.		

#### **Study Design:**

This is an open label, multi-center, Phase II study of BBI608 administered in combination with either Cetuximab, or Panitumumab, or Capecitabine. A cycle will consist of daily and continuous oral administration of BBI608 for four weeks in combination with either Cetuximab, or Panitumumab, or Capecitabine.

Arm A (Cetuximab) - BBI608 is administered at 480 mg po twice daily continuously and Cetuximab will be administered IV on day 5 at 400 mg/m² intravenous infusion over 120 minutes as the initial dose, then weekly at 250 mg/m² over 60-minutes at subsequent cycles.

Arm B (Panitumumab) - BBI608 is administered at 480 mg po twice daily continuously and Panitumumab will be administered IV on day 8 and 22 of each 28 day cycle at 6 mg/kg over 60 minutes.

Arm C (Capecitabine) - BBI608 is administered at 480 mg po twice daily continuously and Capecitabine will be administered orally at  $1000 \text{ mg/m}^2$  bid daily on days 8-21 every three weeks.

6 patients will be initially enrolled in each combination arm at a dose level of 480 mg twice daily (960 mg total daily dose) BBI608. If  $\leq 1$  out of 6 patients have an observable DLT in the combination regimen, then that combination arm may continue to accrue patients. If DLT occurs in  $\geq 2$  of the 6 patients in a combination arm, then the combination arm will closed and no new patients will be enrolled into this combination arm. A trial arm of BBI608 in combination with Cetuximab, or Panitumumab, or Capecitabine will continue to enroll patients only if no more than 1 out of 6 patients for each combination has an observable DLT. It is expected that approximately 60 to 80 CRC patients will be enrolled in the study.

Pharmacokinetics (PK) will be performed in the first cycle for the initial 6 patients of each combination arm of the study.

Pharmacodynamic assessments will be performed in patients with accessible tumors when tumor biopsy is possible.

Evaluation of anti-tumor activity of BBI608 in combination with Cetuximab, or Panitumumab or Capecitabine will be performed at about 8 week intervals while patients remain on study.

To evaluate the tolerability of BBI608, patients from each arm will be assigned to one of 4 sub-cohorts (with 6 patients in each sub-cohort IA, IB, IIA, IIB). The evaluation of tolerability will be done at select centers for the study arm that is continuing patient accrual and in which a total of 50 evaluable patients has not been reached. For each combination arm, patients assigned to sub-cohorts IA and IB will receive BBI608 at 240 mg po twice daily (480 mg total daily dose) starting on day 1 of cycle 1. Intrapatient dose escalation of BBI608 to 480 mg po twice daily (960 mg total daily dose) is allowed as tolerated. Patients assigned to sub-cohorts IIA and IIB will receive BBI608 at 480 mg po twice daily (960 mg total daily dose) starting on day 1 of cycle 1. In case of toxicity, dose adjustment of BBI608 is permitted, as recommended in dose modification guidelines. Additionally, patients assigned to sub-cohorts IA and IIA will receive prophylactic anti-diarrheal treatment starting the day prior to day 1 of cycle 1. Patients assigned to sub-cohorts IB and IIB will anti-diarrheal treatment on an as needed basis starting with development of diarrhea above baseline. For each combination regimen, patients will be sequentially assigned to each of the 4 subcohorts in the following order until 6 patients are accrued on each of the sub-cohorts: IA, IB, IIA, and IIB. If required, up to additional 20 patients may be assigned to selected sub-cohorts to validate the observations in initial 6 patients.

	Sub- cohort	BBI608 Starting Dose Level	Anti-diarrheal Administration	
	IA	240 mg bid (480 total daily dose) 	Prophylactic	
	IB	240 mg bid (480 total daily dose) 	As needed	
	IIA	480 mg bid (960 total daily dose) 	Prophylactic	
	IIB	480 mg bid (960 total daily dose) 	As needed	
	1	ent dose escalation of BBI608 to 480	mg po twice daily (960 mg total	
		) is allowed as tolerated  Stoxicity, dose adjustment of BBI608 is	permitted.	
Study Population:	This study will enroll patients with advanced colorectal cancer. Patients must have received at least 2 lines of standard chemotherapy based on regimens containing 5-FU, irinotecan or oxaliplatin. Patients to be enrolled into the Cetuximab or Panitumumab combination arms must have colorectal cancer with wild-type K-Ras.  Patient accrual will occur over a period of time dependent upon the enrollment rate of the study.			
Test Product, Dose, and Mode of Administration:	Patients in this trial will receive BBI608 orally at 480 mg twice daily (960 mg total daily dose). In each cycle BBI608 will be taken daily for 4 weeks (28 days). BBI608 will be administered twice daily, approximately one hour prior to or two hours after meals with the first dose given in the morning and doses separated by approximately 12 hours.			
	For patients receiving Cetuximab, Cetuximab will be administered IV on day 5 at 400 mg/m² intravenous infusion over 120 minutes as the initial dose, then weekly at 250mg/m² over 60-minutes at subsequent cycles.			
	For patients receiving Panitumumab, Panitumumab will be administered IV on days 8 and 22 of each 28 day cycle at 6 mg/kg over 60 minutes.			
	For patients receiving Capecitabine therapy, Capecitabine will be administered orally at 1000 mg/m  bid daily on days 8-21 every three weeks.			
	Cycles will be repeated until progression of disease, unacceptable toxicity, or another discontinuation criterion is met.			
Duration of Treatment:	continue radiologic most pati	dividual patient, treatment with BBI6 until unacceptable toxicity, discal) or another discontinuation crite ents will receive between one and period of 4 to 16 weeks.	ease progression (clinical or crion is met. It is expected that	

## Criteria for Determination of Dose-Limiting Toxicity:

A DLT is defined by the occurrence of any of the following toxicities possibly or probably related to BBI608, or BBI608 in combination with Cetuximab, or Panitumumab, or Capecitabine within 28 days of treatment:

- CTCAE (Common Terminology Criteria for Adverse Events) Grade 4 hematological toxicity.
- Grade 3 or 4 non-hematological toxicity, except Grade 3 or 4 nausea/vomiting/anorexia, diarrhea, or fatigue will be considered a DLT only if it persists more than three (3) days despite optimal medical management; and alopecia will not be considered a DLT.
- Any other toxicity that in the view of the Principal Investigator represents a clinically significant hazard to the patient.

Whether a DLT has occurred will be assessed during the first 28 days of BBI608 therapy. DLT will be determined from adverse events, changes from baseline in physical examination findings and laboratory parameters. The incidence of adverse events and DLTs will be evaluated for each combination arm and for all patients.

Adverse events considered related to Cetuximab, or Panitumumab or Capecitabine will not be considered DLTs for BBI608 in combination with Cetuximab, or Panitumumab or Capecitabine.

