DLT occurs in  $\geq 2$  of the 6 patients in a combination arm, then that arm of the study will be closed and no further patients will be enrolled. A given arm of the study of BBI608 in combination with Cetuximab, or Panitumumab, or Capecitabine will continue to enroll patients if no more than 1 out of 6 patients in the combination arm has an observable DLT.

Number of Subjects with DLT at 480 mg bid BBI608	DLT Decision Rule
≤ 1 out of 6	Continue patient enrollment in combination arm
≥2 out of 6	Close combination arm of the study

The following number of colorectal cancer patients will be enrolled based on a two-stage Simon design with an alpha of 5% and a power of 80% to detect a disease control rate improvement for Cetuximab and Panitumumab from about 30% (historical DCR for 3rd and 4th line colorectal cancer) to 60%, and a disease control rate improvement for Capecitabine from about 15% (historical DCR for 3rd line colorectal cancer) to 60%.

Table 1 Simon two-stage design for Phase II

	Patient number				
Combo Therapy	Stage 1	Stage 2	Total*		
Cetuximab	8	16	24		
Panitumumab	8	16	24		
Capecitabine	6	12	18		

\*If any of the three arms reach a DCR of 60% or more at the end of Simon Stage 2, a one-time option to expand accrual to a total sample size of up to 50 patients may be implemented for each arm.

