# 4.5 Dose-Limiting Toxicity

Dose-limiting toxicity is defined by the occurrence of any of the following toxicities possibly or probably related to BBI608 in combination with Cetuximab, or Panitumumab or Capecitabine within 28 days of treatment. DLT will be scored during the 28 days of BBI608 treatment.

- Grade 4 hematological toxicity
- Grade 3 or 4 non-hematological toxicity, except:
  - o Grade 3 or 4 nausea/vomiting/anorexia, diarrhea and fatigue will be considered a DLT only if it persists more than three (3) days despite optimal medical management
  - o Alopecia will not be considered a DLT

Adverse events considered related to Cetuximab, or Panitumumab or Capecitabine will not be considered DLTs.

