3.2. Secondary Endpoints

- PK parameters of napabucasin administered in combination with cetuximab, or panitumumab, or capecitabine.
- PK parameters of capecitabine and metabolite (5-FU).
- Pharmacodynamics parameters (or biomarkers) of napabucasin administered in combination with cetuximab, or panitumumab, or capecitabine. Response (increase or decrease) of several biomarkers of napabucasin from biopsied tumors following napabucasin administration will be examined in patients with accessible tumors who consent to an optional biopsy.
- Objective Response Rate (ORR)

ORR is defined as the percentage of patients with a best overall response (BOR) of complete response (CR) or partial response (PR). The categorizations of response (CR, PR, SD, PD, and NE) and the derivations of BOR is provided in Appendix 1.1 and 1.2.

• Progression Free Survival (PFS) and Overall Survival (OS)

PFS is defined as the time from the date of first treatment (or date of enrollment in sensitivity analysis) to the date of first documentation of progressive disease (PD) or death due to any cause, whichever occurs first.

OS is defined as the time from the date of treatment (or date of enrollment in sensitivity analysis) to the date of death. Patients without documentation of death at the time of analysis will be censored at the date last known to be alive.

• Dose Limiting Toxicities (DLTs): For definition of DLT, see Section 4.5 of the protocol amendment 2 [5].

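### The protocol defines DLT in two conflicting ways, in the synopsis and in Section 4.5, so the same six patients could close an arm under the first and leave it open under the second

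*Protocol*

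**What the plan says.** **Protocol synopsis, criteria for DLT.** Three criteria are listed: Grade 4 hematological toxicity; Grade 3 or 4 non-hematological toxicity with stated exceptions; and "Any other toxicity that in the view of the Principal Investigator represents a clinically significant hazard to the patient". The attribution clause covers toxicities "possibly or probably related to BBI608, or BBI608 in combination with Cetuximab, or Panitumumab, or Capecitabine within 28 days of treatment".

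**Protocol Section 4.5.** Only the first two criteria appear. The list ends with the exception "Alopecia will not be considered a DLT" and has no investigator-judgement item. The attribution clause reads "possibly or probably related to BBI608 in combination with Cetuximab, or Panitumumab or Capecitabine within 28 days of treatment", so BBI608 alone is not named. The window is given as "DLT will be scored during the 28 days of BBI608 treatment".

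**Closure rule, protocol Section 4.1.** An arm continues if no more than 1 of 6 patients has a DLT. If DLT occurs in two or more "of the 6 patients in a combination arm, then that arm of the study will be closed and no further patients will be enrolled". The synopsis and SAP Section 4.2.1 use the same thresholds.

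**SAP.** Section 3.2 makes DLT a secondary endpoint and says "For definition of DLT, see Section 4.5 of the protocol amendment 2". Section 8.2.3.4 promises a listing of DLTs by arm and cohort.

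**The concern.** The DLT count is the only input to a rule that closes or continues a whole treatment arm, and the rule turns on the difference between 1 and 2 patients. Two texts in the same protocol define that count differently, with no order of precedence. For example, a Grade 3 hematological toxicity that the investigator regards as a clinically significant hazard is a DLT in the synopsis and is not one in Section 4.5.

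The definition also touches protocol Section 11.3, which allows replacement of a patient who does not receive four weeks of BBI608 for a reason other than DLT. A patient stopped early by a synopsis-only event counts as a DLT under one text and may be replaced under the other.

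Safety is part of the primary objective, and protocol Section 10.7 promises DLT incidence by arm and overall. If a reader cannot tell which definition was applied, neither that incidence nor the reason an arm continued or closed can be reconstructed.

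**Working it through.** **1. Text comparison.**

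| Element | Synopsis | Section 4.5 |
|---|---|---|
| Grade 4 hematological | yes | yes |
| Grade 3-4 non-hematological, three-day and alopecia exceptions | yes | yes |
| Investigator-judged hazard | yes | absent |
| Attribution | BBI608, or BBI608 in combination | BBI608 in combination |
| 28-day window | yes | yes |
| Events related to the combination drug excluded | yes | yes |

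The conflict lies in the third and fourth rows; the others agree in substance. Every Section 4.5 DLT is also a synopsis DLT, so the synopsis count is never the smaller. The disagreement can only take the form: closed under the synopsis, open under Section 4.5.

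**2. A case that needs no assumed rate.** Of six patients, one has a Section 4.5 DLT and another has only an event meeting the third synopsis criterion. The synopsis counts 2 of 6 and the arm closes. Section 4.5 counts 1 of 6 and the arm continues.

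**3. When one synopsis-only patient matters.** The decision changes only if exactly one of the other five has a Section 4.5 DLT. With none, the count is 1 and the arm continues under both texts; with two or more, it closes under both. At an assumed per-patient rate p the chance is 5p(1 − p)^4:

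- p = 0.20: 5 × 0.20 × 0.80^4 = 41%
- p = 0.05: 5 × 0.05 × 0.95^4 = 20%

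**4. Chance of opposite decisions.** The documents state no DLT rate and no operating characteristic for the rule, so there is no plan figure to reproduce. Two rates are assumed: p, the per-patient rate of Section 4.5 DLTs, and q, the added rate of patients whose only DLT is a synopsis-only one. Patients are taken as independent, and the same six are judged under both texts (replacement under Section 11.3 is left out).

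The closure probability at rate r is C(r) = 1 − (1 − r)^6 − 6r(1 − r)^5. Because one set of DLTs contains the other, the probability of opposite decisions is C(p + q) − C(p).

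Worked example, p = 0.10 and q = 0.10:

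- C(0.10) = 1 − 0.5314 − 0.3543 = 11.4%
- C(0.20) = 1 − 0.2621 − 0.3932 = 34.5%
- difference = 23.0 percentage points, before rounding of the two terms

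Probability of opposite decisions over the range:

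| p | q = 3% | q = 5% | q = 10% | q = 15% |
|---|---|---|---|---|
| 5% | 4.5% | 8.1% | 19.1% | 31.2% |
| 10% | 6.3% | 10.9% | 23.0% | 35.2% |
| 15% | 7.2% | 12.1% | 24.3% | 35.6% |
| 20% | 7.3% | 12.1% | 23.5% | 33.6% |

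The result depends much more on q than on p, and q is the quantity about which the documents say least.

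**The case against.** A reader might infer that a single synopsis-only event is enough to reverse an arm decision. It is not: step 3 shows that it needs exactly one other patient with a Section 4.5 DLT, and at the assumed rates of 5% and 20% that happens less than half the time.

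The assumed rates can also be challenged. Protocol Section 4.3 reports Phase I escalation to 2000 mg per day without dose-limiting toxicity and with generally mild events. That was monotherapy and does not settle the rate in combination, but it is a reason not to rest the point on any single pair of rates. Only the range is offered here, and it is illustrative.

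A reader might also infer that the SAP's citation of Section 4.5 drove arm closures, or that the SAP listing will certainly leave synopsis-only events out. The documents support neither. The SAP is dated 2018 to 2020, and its Section 2.1 describes the six-patient rule largely in the past conditional, so the citation bears mainly on reporting; the decision risk comes from the protocol itself. SAP Section 8.2.3.4 does not say whether DLTs are re-derived or listed as recorded at the time, and the underlying event should still appear among the adverse events.

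These objections limit the size and reach of the point. They do not remove it: both lists are complete on the page, one whole criterion and part of the attribution wording differ, and nothing says which governs.

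**Conclusion.** The point holds as a contradiction within the protocol, carried into the SAP by its citation of Section 4.5. It affects the only input to the arm-closure rule and runs one way, towards closure under the synopsis. Under assumed rates of 5-20% for Section 4.5 DLTs and 3-15% for added synopsis-only DLTs, the two texts disagree on the same six patients with probability 4.5% to 35.6%. The contradiction itself needs no assumption; the percentages rest entirely on these rates and on independence between patients.

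For reporting the conclusion is conditional: if the SAP listing is derived from Section 4.5, it could omit an event that counted as a DLT under the synopsis. That the supplied protocol is the amendment 2 cited by the SAP is inferred from its 480 mg dose and its sub-cohorts. The point deserves correction because the change is small and the rule it feeds can close an arm.

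**What to change.** Reconcile the synopsis and protocol Section 4.5 to a single DLT definition, covering both the list of criteria and the attribution wording, and have SAP Section 3.2 cite it. Which text is right is for the sponsor and investigators to settle; no view is taken here.

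In the SAP Section 8.2.3.4 listing, state whether DLTs are re-derived or taken as recorded. Where the investigator's judgement was recorded, flag events that meet only the synopsis criterion and show each arm's count out of 6 with and without them. Reconciled wording cannot change decisions already taken, so this display lets a reader see whether the choice of definition mattered.

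The cost is a wording alignment and one flag in a listing already planned. The flag depends on the hazard judgement having been captured, which the documents do not show; if it was not, the listing should say so.

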# Pharmacokinetic and Pharmacodynamic Variables:

Pharmacokinetic variables to be determined include maximum plasma drug concentration (Cmax), volume of distribution, area under the time-concentration curve (AUC), distribution half-life, and terminal half-life. Blood samples for PK determination will be drawn on Days 5-12 and Days 26-33 for the Cetuximab arm, on Days 8-15 and 22-29 for the Panitumumab arm, and on Days 8-9 and Days 21-22 for the Capecitabine arm during the first cycle for the first 6 patients in each combination arm. Response (increase or decrease) of several biomarkers from biopsied tumors following BBI608 administration will be examined in patients with accessible tumors for biopsy. Tumor biopsies will be collected prior to the first dose of BBI608 and on day 8 of the first cycle for patients with accessible tumors and who have signed the optional tumor biopsy consent.

#### **Statistical Methods:**

In general, categorical variables will be summarized as the number and percentage of patients in each category. Continuous variables will be summarized by the mean, standard deviation, median, minimum, and maximum.

The primary population for the efficacy evaluation will be the evaluable population, defined as patients who have been treated with at least 80% of 1 complete cycle of BBI608 and a combination drug. The primary endpoint will be disease control rate, defined as the proportion of patients with a documented complete response, partial response and stable disease (CR + PR + SD) based on RECIST. The secondary endpoints will include progression-free survival (PFS) and overall survival (OS). PFS will be calculated from the date of patient enrolment into the trial until documented disease progression based on RECIST. OS will be calculated from the date of patient enrolment into the trial until death.

Patient sample size for each combination regimen is calculated based on a power of 80 and a one-sided alpha of 5% to detect a disease control rate improvement for Cetuximab and Panitumumab from about 30% (historical DCR for 3rd and 4th line colorectal cancer) to 60% and for Capecitabine from about 15% (historical DCR for 3rd line colorectal cancer) to 60%.

Safety analyses will include adverse events, SAEs, laboratory tests, and physical examination changes from baseline. The safety population will include all patients who have received any amount of BBI608 and the combination drug. All patients receiving at least one daily dose of BBI608 will be considered evaluable for safety analyses. In addition to the evaluation and categorization of adverse events, listings of laboratory test results collected at baseline and during the study will be generated. Descriptive statistics summarizing the changes in those laboratory tests over time will be presented.

Analysis and Sample size for sub-cohorts:

Each sub-cohort will be analyzed for number of days of Grade II/III diarrhea and % treatment compliance achieved during the first two cycles. The % treatment compliance will be calculated as the number of capsules actually ingested over the number of capsules that should have been ingested per dose level multiplied by 100. The research questions addressed by sub-cohorts are hypothesisgenerating and exploratory in nature. Initially 6 subjects will be assigned to each sub-cohort to assess the effect of intervention. Selected sub-cohorts will be extended to enroll up additional 20 patients. The decision of extending the enrollment will be based on clinical assessment without formal statistical testing. However, 20 patients will give 80% power to detect 20% difference in % treatment compliance between two arms and 57% power to detect the difference of 25% in the number of days of having Grade II/III diarrhea using two-sided Z test with pooled variance at type I error rate of 0.15. The control rates assumed are 70% for treatment compliance and 30% for diarrhea. The patients will be sequentially allocated to different sub-cohorts by the Sponsor to avoid section bias.

